7.5.1 Analysis of Safety

The primary analysis is of safety that will include any patients who receive at least one dose of Lapatinib and/or Veliparib. The treatment related toxicity rate will be estimated at the end of the study along with two sided 95% exact confidence intervals ([Clopper-Pearson intervals](#)). Analysis of safety data will be descriptive. Descriptive statistics will be calculated for quantitative safety data and frequency counts will be compiled for classification of qualitative safety data. Adverse event and serious adverse event (AE/SAE) (AE/SAE definition is in 9.1.1) reporting during the study will be summarized by relationship to study drug and intensity. Number and proportion of adverse event, serious adverse event and grade 3 or 4 lab toxicity will be reported by body system and by each study arm. Patient's baseline lab data and its change during treatment at each visit will be presented. Graphic statistics tool such as box plot will be used when it is appropriate.

7.5.2 Analysis of Efficacy endpoints

At the completion of the study, the secondary endpoint of ORR rate will be estimated along with two-sided 95% confidential intervals for Lapatinib and Veliparib combination group with exact method of [Clopper-Pearson intervals](#). Secondary endpoint analysis will be descriptive. Mean, median, and range will be used to describe continuous demographic variables. Frequency and proportion will be used to describe categorical variables. The K-M estimator will be used to estimate median progression free survival along with 95% confidence intervals.

Exploratory analysis will be conducted on the correlations between clinical outcomes and biomarkers or gene expression profiles. Gene expression profile, proliferation/apoptosis markers, and circulating level of tumor cells will be analyzed between responders and non-responders using two-sample t-test test assuming normal distribution for gene expression level. An appropriate normal transformation will be conducted prior analysis when it is necessary. Alternatively, one way analysis of variance (ANOVA) can be used to evaluate gene expression and biomarkers by responders. Logistic regression analysis will be used to predict response with these genes or biomarkers with or without adjustment for covariate, e.g. age. Two-sample log rank test will be used to compare PFS curves classified by biomarkers or gene expression profiles so that potential prognostic biomarkers or genes will be identified. Multivariate Cox proportional hazards model will be used to identify a set of biomarkers for prediction of time to disease progression between responders and non-responders. Hazards ratios with 95% confidence intervals will be calculated for each significant biomarker in terms of predicting time to disease progression. Since this is an exploratory pilot study which will be used as a hypothesis generator. We will include EGFR expression and location, and markers of apoptosis and DNA repair as covariate in all above

exploratory analysis.

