This rule will provide a probability of 0.10 of stopping early if the true toxicity rate is 30%. In that case the expected number of subjects on the trial will be 18.87 and the expected number of toxicities will be 5.7. If, on the other hand, the true toxicity rate is 60%, then the probability of stopping early is 0.87 with an expected sample size of 9.8 and 5.9 expected toxicities. Table 2 is the stopping guideline if 'X' out of 'N' has a pre-defined toxicity. As an example, if we enroll 3 patients and all have toxicity, then we will consider stopping the trial; if we enroll 6 patients and 5 patients have toxicity then the trial will be stopped.

Drug related toxicities for the safety analysis described above are defined as: a) any grade 3 or 4 non-hematologic toxicity except anorexia, alopecia, nausea, fatigue, fever without neutropenia; b) failure to recover to baseline (except alopecia) after delaying the next dose by more than 14 days; c) grade 3 or 4 neutropenia complicated by fever $\geq 38.5^0$ C or infection, or grade 4 neutropenia of at least 7 days duration; or d) grade 4 thrombocytopenia, or grade 3 thrombocytopenia complicated by hemorrhage. Toxicity evaluation of the patients enrolled in the trial will be done using the NCI Common Toxicity Criteria, Version 4.0, and will be presented to the Clinical Protocol Monitoring Committee (UAB Safety and Monitoring Plan).

If toxicity meets the stopping rule at any time during the first 5 patients enrolled in the pilot study (see table 2), the protocol will allow the investigators to open a new 20 patient cohort using Lapatinib 1000 mg PO a day and Veliparib 150 mg PO twice a day. The new cohort will follow the same rules used in the original cohort (Cohort -1). Patients developing grade 1 and 2 toxicities will be permitted to take a drug holiday of up to 14 days; after the drug holiday, if the adverse event has resolved to the satisfaction of the investigator, the study drugs may be resumed at the same level. In the event of recurrent toxicity, there will be one dose reduction permitted (dose reduction minus one will be Lapatinib 750 mg PO daily continuously and Veliparib 100 mg PO every 12 hours continuously). If the adverse event recurs after dose reduction two, the patient will be taken off the study.

Patient Selection Criteria

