A tumor biopsy of one of the metastatic lesions (see eligibility criteria for biopsy guidelines) will be obtained before initiation of therapy. Biopsy samples will preferably be obtained using a 14-18 gauge core needle; **at least** two core biopsies will be obtained and snap frozen individually for gene expression; a **third** core will be used for the preparation of paraffin-embedded blocks or formalin fixed tissue.

Biopsy of a metastatic lesion is not required for protocol entry but all patients with reasonably accessible lesions (chest wall, breast, skin, subcutaneous, superficial lymph nodes, bones and liver metastases) must agree to biopsy. Lung biopsies are not acceptable for research only. Biopsies may be done with local anesthesia or intravenous conscious sedation, according to standard institutional guidelines. If a biopsy requires general anesthesia, then it is only allowed **if** acquisition of tissue is necessary for clinical reasons (i.e. is clinically indicated), and excess tissue that would otherwise

have been discarded is then used for research purposes. If a biopsy requires general anesthesia, then a biopsy of that site for research purposes only, *without* a coexisting clinical indication is not allowed on this protocol. Patients with reasonably accessible lesions as described above, who will not agree to the biopsy, will not be enrolled in the trial. Patients with NO reasonably accessible lesions as described above can be enrolled in the trial.

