Two of the snap frozen research biopsies will be sent to [name] laboratory located at the Hazelrig Salter Radiation Oncology Center ([name], [contact], lab pager [name]) where biopsies will be stored for batching. All samples will be indelibly labeled with the appropriate study number, and date of acquisition; these data will be correlated with clinical efficacy including complete response and objective response. One of the frozen research biopsies will be processed for targeted gene expression analysis, tumor microRNA profiling, and copy number variation of commonly amplified or deleted genes in cancer using the Nanostring nCounter DX system with FLEX configuration ([name] Lab). This system will also allow for the analysis of the Prosigna Breast Cancer Prognostic Gene Signature Assay (based on the PAM50 gene set established by Charles Perou et al., *Nature* 2000) that provides intrinsic subtyping information as well as prognostic information as it relates to drug response. Targeted gene expression will be performed using prebuilt gene panels by Nanostring including the Human Kinase (519 kinases), Human Immunology (594 immunology genes), Human Cancer Reference (236 cancer related genes), and Human Inflammation (184 inflammation gene) kits. Tumor microRNA profiles will also be analyzed using total RNA from tumor biopsies (800 human miRNAs). Lastly, copy number variation of commonly altered genes in cancer will be investigated from DNA harvested from the tumor. For each analysis, as little as 100ng of total RNA or 300ng of genomic DNA is needed for highly reproducible results. Additionally, if available, formalin-fixed paraffin-embedded tissues from the original primary tumor will also be subjected to this analysis to investigate the evolution of the tumor from primary to metastatic.

Fifteen slides will also be prepared from the formalin-fixed paraffin embedded tissue for analysis by conventional IHC of ER, PR, Her-2, EGFR, PARP, Ki67, apoptotic markers, and biomarkers of DNA repair such as H2AX, PARP, and BRCA localization. All samples will be indelibly labeled with the appropriate study number, and date of acquisition; these data will be correlated with clinical efficacy including complete response and objective response.

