7.0 STATISTICAL CONSIDERATIONS

This is an open-label, single arm, single institution, pilot clinical trial. The primary objective is to characterize the safety profile and treatment tolerance of Veliparib (ABT-888) in combination with Lapatinib (Tykerb) in patients with metastatic, estrogen receptor (ER) negative, progesterone receptor (PR) negative, and human epidermal growth factor receptor 2 (HER-2-Neu) negative breast cancer. Secondary objectives will estimate the objective response rate (ORR) (complete responses [CRs] plus partial responses [PRs]); Determine progression free survival (PFS); correlate pre-treatment tumor gene expression profile, biomarkers of DNA repair (H2AX, BRCA localization), EGFR location and signaling, and apoptosis markers with the ORR and PFS; Correlate serial measures of CTCs and serum levels of M30 with the ORR and PFS and determine the pharmacokinetics of Veliparib and Lapatinib when given in combination. A total of 20 (maybe 25 if an additional cohort is added) patients will be enrolled in a single site (University of Alabama at Birmingham) over a projected 12-18 months accrual interval.

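### Hazard ratios are promised for biomarkers found significant, with no significance level or multiplicity control for a screen of up to about 2,300 features in 20 to 25 patients

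*Combined protocol and SAP*

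**What the plan says.** Section 7.5.2 plans t-tests or ANOVA and logistic regression for response. For PFS it plans two-sample log-rank tests, so that "potential prognostic biomarkers or genes will be identified", and a multivariable Cox model to pick out a set of biomarkers. The reporting rule follows: "Hazards ratios with 95% confidence intervals will be calculated for each significant biomarker in terms of predicting time to disease progression". Sections 7.0 to 7.6 give no alpha for this work, no candidate list, no cut-points, no selection rule and no multiplicity method. The only adjustment mentioned is for covariates. The section calls the work exploratory and hypothesis-generating. It makes EGFR, apoptosis and DNA-repair markers covariates throughout.

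Section 6.3 gives the size of the tissue screen: "Human Kinase (519 kinases), Human Immunology (594 immunology genes), Human Cancer Reference (236 cancer related genes), and Human Inflammation (184 inflammation gene) kits", and "Tumor microRNA profiles will also be analyzed using total RNA from tumor biopsies (800 human miRNAs". It also plans sequencing-based assays, for which no feature count is stated.

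On numbers, section 7.0 says "A total of 20 (maybe 25 if an additional cohort is added) patients will be enrolled in a single site". The 25 fits section 3.0: if the stopping rule is met within the first 5 patients, "the protocol will allow the investigators to open a new 20 patient cohort" (5 + 20 = 25). Tissue may come from fewer, because "Patients with NO reasonably accessible lesions as described above can be enrolled in the trial".

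**The concern.** A 95% interval covers the truth 95% of the time when it is reported regardless of its result. If it is shown because the marker passed a significance screen, that guarantee is lost, and the estimates that pass are pushed away from 1. With many features, few patients and no error-rate control, the printed hazard ratios will mix true and chance findings, and a reader cannot judge the mix without the number tested.

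The rule also bears on the stated objectives. Section 1.2 names EGFR location and signaling, H2AX, BRCA localization, apoptosis markers and serum M30 for correlation with response and PFS. An estimate and interval for each is useful whatever its p-value, yet the plan promises one only on significance.

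**Working it through.** The plan states no figure for the biomarker analysis. Its only sample-size figures, the exact 95% intervals at N = 20 in section 7.4, reproduce: 4/20 gives 5.73 to 43.66%, 5/20 gives 8.66 to 49.10%, and 6/20 gives 11.89 to 54.28%. They concern event rates and say nothing about biomarkers.

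**Inputs from section 6.3.** Panel genes: 519 + 594 + 236 + 184 = 1,533, if the panels do not overlap. With 800 microRNAs: 2,333.

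**Assumptions not in the documents.** Two-sided alpha 0.05 (suggested by the 95% intervals); even-split groups; 20 PFS events, with a range of 12 to 25; true hazard ratios of 1.5 to 4.

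**1. Expected chance hits for PFS if no feature is associated** (number of features × 0.05; correlation does not change the expectation):
- panel genes: 1,533 × 0.05 = 76.65, about 77
- with microRNAs: 2,333 × 0.05 = 116.65, about 117
- even for 10 independent markers, the chance of at least one is 1 − 0.95^10 = 0.40

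**2. Power per feature.** SE of log HR = 2/√20 = 0.447, so significance needs an observed HR of at least exp(1.96 × 0.447) = 2.40 (or its reciprocal). Power = Φ(ln HR/0.447 − 1.96), which is 0.15 at HR 1.5, 0.34 at HR 2 and 0.69 at HR 3.

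**3. False share of hits.** With π the truly prognostic share, false share = 0.05(1 − π) / [0.05(1 − π) + π × power]:

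| π | HR 2 | HR 3 |
|---|---|---|
| 1% | 94% | 88% |
| 5% | 74% | 58% |
| 10% | 57% | 39% |
| 20% | 37% | 22% |

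Half the hits are false when π = 0.05/(0.05 + power): 0.05/0.391 = 12.8% at HR 2 and 0.05/0.740 = 6.8% at HR 3. Over 12 to 25 events and HR 1.5 to 4, this break-even runs from 5% to 32%.

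**4. Coverage of the 95% interval given significance.** This takes the interval and the test to correspond.
- Null marker: it is selected only when its interval excludes 1, so coverage is 0%.
- True HR 2: ln 2/0.447 = 1.55. The interval covers, and the marker is significant, when z lies between 1.96 and 3.51, with probability 0.975 − Φ(0.41) = 0.316. Divided by 0.341 this is 93%.
- In the same way: 82% at HR 1.5 and 96% at HR 3.
- Averaged over all hits from 2,333 features: with 5% true at HR 2 there are about 111 false and 40 true hits, so 0.926 × 40/151 is about 24%. With 20% true at HR 3 there are about 93 false and 322 true, so 0.964 × 322/415 is about 75%.

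**5. Exaggeration.** By simulation with 20 events, a true HR of 1.5 that passes is reported at a median of about 2.9 (on the scale above 1).

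**6. Strict correction as an alternative.** Bonferroni sets alpha at 0.05/2,333 = 2.1 × 10⁻⁵. Power at 20 events is then 0.3% at HR 2, 3.7% at HR 3 and 12.5% at HR 4, so almost nothing is detectable.

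**The case against.** The strongest reply is that section 7.5.2 declares the work exploratory, and no trial decision rests on it. The primary endpoint is safety, and section 7.4 ties the phase II proposal to a response rate of at least 30%. This stands, and it limits the importance of the point. The label excuses low power and lack of confirmation, but it does not restore the coverage of intervals chosen by significance.

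Second, the screen may be narrower than a test of every feature. Section 7.5.2 speaks of expression profiles and one multivariable model, and the candidate set for the hazard ratios is undefined. It does not name microRNAs, and section 6.3 names only response outcomes for the tissue data, without excluding PFS. So 77 is the firmer figure, and 117 needs the microRNAs to enter the PFS screen. A reader might double 117 to cover response as well, but response analyses yield no hazard ratio.

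Third, a reader might infer that the named markers could disappear from the report. The documents do not support that. They are covariates in the exploratory models, their correlation with outcome is a secondary objective, and the response comparisons carry no significance filter. The reporting sentence does not say that other hazard ratios will be withheld. At worst, a non-significant marker lacks a reported hazard ratio and interval.

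**Conclusion.** The point holds as a defect in the reporting rule. Hazard ratios and intervals are tied to an undefined significance, with no multiplicity control, over up to 1,533 panel genes and 800 microRNAs in 20 (possibly 25) patients. At an assumed two-sided 0.05 with nothing associated, 77 to 117 chance hits for PFS are expected, and the selected intervals under-cover as a set.

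Two stronger readings are not supported. A reader might infer that most reported hits must be false. With 20 events that needs a truly prognostic share below about 13% at HR 2 or 7% at HR 3, and the documents give neither share nor effect size. A reader might also infer that every reported interval is invalid, but a single strong true marker keeps coverage of about 93 to 96%.

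The primary safety analysis and the response-based phase II trigger are untouched. The figures rest on the assumed alpha, event count, even split and effect sizes, and on no overlap between panels.

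**What to change.** In section 7.5.2:

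- Report the hazard ratio and 95% interval for every individually named marker in section 1.2 that is measured, regardless of its p-value.
- For the genomic panels, replace the word significant with a stated false discovery rate criterion, such as Benjamini-Hochberg at a level fixed in advance.
- Report the number of features tested and all q-values.
- Label nominal panel intervals as exploratory and not adjusted for selection.

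The cost is SAP text and routine software, with no change to patients, sample size or data collection. The downside is fewer panel hits, possibly none.

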7.2 Secondary Endpoint

In patients with metastatic TNBC, who will be treated with the combination of Veliparib and Lapatinib, we will estimate the ORR (CRs plus PRs); determine PFS; correlate pre-treatment tumor gene expression profile, biomarkers of DNA repair (H2AX, BRCA localization), EGFR location and signaling, and apoptosis markers with the ORR and PFS; correlate serial measures of CTCs and serum levels of M30 with the ORR and PFS; determine the pharmacokinetics of Veliparib and Lapatinib when given in combination.

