7.4 Sample Size and Power Justification

This is a single arm pilot study to evaluate the safety of combination of Veliparib and Lapatinib in patients with metastatic TNBC. A total of 20 patients will be enrolled to evaluate the safety as treatment related toxicity rate and the objective response rate. The sample size is NOT determined by the statistical power but the feasibility and relative precision of estimate, e.g. standards error of the estimation is $\leq 10\%$. Assuming the acceptable toxicity rate with combination therapy is no more than 30%; then, we will be able to have two sided 95% exact confidence intervals ([Clopper-Pearson intervals](#)) of toxicity estimate from 11.8% to 54.3%. Meantime, this sample size will provide two-sided 95% exact confidence intervals ([Clopper-Pearson intervals](#)) of objective response rate estimation as follow:

Table 2 Exact 95% Confidence Interval for Response Rate Estimation

Response rate %	Confidence interval (lower) %	Confidence interval (Upper) %
20	5.73	43.66
25	8.66	49.10
30	11.89	54.28

If the response rate is equal or greater than 30%, we will propose a phase II trial to be conducted in the Translational Breast Cancer Research Consortium (TBCRC).

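### Section 7.5.2 requires four or more biomarker covariates in all exploratory analyses; this conflicts with its own paragraph and leaves about one responder or fewer per logistic term

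*Combined protocol and SAP*

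**What the plan says.** Section 7.5.2 (Analysis of Efficacy endpoints) lists these exploratory methods: two-sample t-test or one-way ANOVA between responders and non-responders, logistic regression for response, two-sample log-rank test for PFS, and a multivariable Cox model. On the logistic model it says "Logistic regression analysis will be used to predict response with these genes or biomarkers with or without adjustment for covariate, e.g. age". The paragraph describes the work as hypothesis-generating and then closes with "We will include EGFR expression and location, and markers of apoptosis and DNA repair as covariate in all above" exploratory analysis.

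Section 7.2 (Secondary Endpoint) gives the same markers as objects of study. The plan will correlate, among other things, "biomarkers of DNA repair (H2AX, BRCA localization), EGFR location and signaling, and apoptosis markers with the ORR and PFS".

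On numbers, section 7.4 says "A total of 20 patients will be enrolled to evaluate the safety as treatment related toxicity rate and the objective response rate", and section 7.0 says "A total of 20 (maybe 25 if an additional cohort is added) patients will be enrolled in a single site". Section 7.4 also tabulates exact intervals for response rates of 20%, 25% and 30%. Section 6.3, on biopsies, says "Patients with NO reasonably accessible lesions as described above can be enrolled in the trial".

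Section 7.5.2 does not say how many markers count as covariates. It sets no limit on model terms, names no penalised or exact method, and gives no rule for a fit that fails.

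**The concern.** The closing sentence is an instruction, and it raises four difficulties.

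- It conflicts with the optional adjustment stated for logistic regression earlier in the paragraph.
- It cannot be carried out for a two-sample t-test or a two-sample log-rank test, which take no covariates.
- It treats EGFR location, apoptosis and DNA-repair markers as adjusters, although sections 1.2 and 7.2 set them up as the markers to be related to ORR and PFS.
- Where it can be carried out, in the logistic model, it puts 5 or more terms on a handful of responders. If some combination of terms separates responders from non-responders, no finite maximum-likelihood estimate exists and the software reports a meaningless, very large odds ratio. Fits that do converge rest on about one responder per term and are unstable.

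At stake is the adjusted part of the biomarker-response objective in a pilot meant to inform a phase II trial.

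**Working it through.** **1. Responders.** The table in section 7.4, "Exact 95% Confidence Interval for Response Rate Estimation", covers 20%, 25% and 30% of 20 patients: 0.20 × 20 = 4, 0.25 × 20 = 5, 0.30 × 20 = 6. Clopper-Pearson limits recomputed from beta quantiles are 5.73-43.66% for 4/20, 8.66-49.10% for 5/20 and 11.89-54.28% for 6/20. These match the plan's table.

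**2. Model terms.** The closing sentence of 7.5.2 implies at least EGFR expression + EGFR location + one apoptosis marker + one DNA-repair marker = 4 covariates. Section 7.2 names two DNA-repair markers (H2AX, BRCA localization), which gives 5. A second apoptosis marker gives 6. Adding the gene or marker under test gives 5, 6 or 7 terms.

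**3. Responders per term.**
- 5 terms: 4/5 = 0.8 to 6/5 = 1.2
- 6 terms: 4/6 = 0.67 to 6/6 = 1.0
- 7 terms: 4/7 = 0.57 to 6/7 = 0.86

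**4. How often the fit has no finite solution.** Code s = +1 for a responder and −1 for a non-responder. The data are separated, completely or quasi-completely, if some non-zero (b0, b) gives s(b0 + x′b) ≥ 0 for every patient, with at least one strict inequality. This was tested by linear programming: maximise the sum of s(b0 + x′b) subject to those inequalities, with every coefficient between −1 and 1. An optimum above zero means separation. Markers were independent standard normal with no effect on response. For n = 20, run A used 2,000 data sets per cell and run B is a separate repeat:

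| Terms | Run | 6 responders | 5 responders | 4 responders |
|---|---|---|---|---|
| 5 | A | 5.5% | 9.7% | 16.8% |
| 5 | B | 6% | 9% | 17% |
| 6 | A | 14.2% | 20.5% | 32.2% |
| 6 | B | 13% | 17% | 36% |
| 7 | A | 26.4% | 37.9% | 55.7% |
| 7 | B | 29% | 36% | 52% |

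With one continuous marker the rate is about 0% (at most 0.2%). The runs differ by up to 4 percentage points, which is simulation error.

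**5. Sensitivity.**
- 25 patients, 5-7 responders: 1-5% with 5 terms, 3-12% with 6, 7-24% with 7. A repeat gave 1-23% overall.
- 15 patients with tissue (an assumption; the plan gives no number), 3-5 responders: 22-50%, 43-74% and 63-90%. A repeat gave 24-87% overall.
- All markers binary, n = 20, 4-6 responders: 27-59% with 5 terms, 39-71% with 6. A single binary marker gives 3-13%.
- Each marker shifted by 0.5 SD in responders: 23-41% with 5 terms, 46-63% with 6.
- 3 responders of 20: about 32% with 5 terms, 54% with 6. At a true response rate of 20%, the chance of 3 or fewer responders is 41%.

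**6. Shared covariates.** The same covariates enter every gene's model. If they separate the data on their own, every adjusted logistic fit fails together. From run A, 4 covariates alone do so in 1.9%, 3.1% and 7.3% of data sets (6, 5, 4 responders), and 5 covariates alone in 5.5%, 9.7% and 16.8%. The panels in section 6.3 list 519 + 594 + 236 + 184 = 1,533 entries, with unknown overlap.

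**The case against.** The strongest reply is that the sentence is loosely worded and means less than it says. Logistic regression is expressly allowed without adjustment. Sections 1.2 and 7.2 treat these markers as explanatory variables, so including them in all the analyses may only mean that each method is applied to each of them. That covariates are impossible in a t-test or log-rank test favours this milder reading. It may be what was intended, but the sentence says covariate, and an analyst who follows it literally gets the models described here. The text needs correcting either way.

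Several stronger conclusions that a reader might draw are not supported:

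- *At least five covariates are forced.* The plan fixes only about four. On that count most adjusted fits (about 83-94% at n = 20) do have a solution.
- *There can be at most 20 patients.* Section 7.0 allows 25. Pooling them would mix two starting doses (section 3.0), and it lowers the failure rate without removing the problem.
- *Many patients will lack tissue.* Section 4.1 requires biopsy of accessible lesions, and the number without one is not given. Serum M30, an apoptosis marker, needs no biopsy.
- *The Cox models fail as well.* No rate was computed for them. PFS events are progressions or deaths and could well exceed 4-6.
- *The biomarker objective would fail.* Unadjusted t-test or ANOVA, log-rank and logistic analyses remain. The phase II trigger in section 7.4 is a response rate of 30% or more, not a biomarker model.

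The exploratory label limits the consequence. It does not help when an estimate does not exist.

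**Conclusion.** Wrong as written, and confined to the exploratory analyses. The covariate sentence contradicts the optional adjustment beside it, cannot be applied to two of the listed tests, and makes adjusters of the markers under study. Followed in the logistic model, it gives no finite estimate in roughly one fit in 17 to one in two at the planned size. Where in that range depends on a marker count the plan leaves open and on how many patients respond. The result rests on the plan's 4-6 responder scenarios and on independent, continuous, null markers; binary markers, real effects or missing tissue raise the rate, and 25 pooled patients lower it. The adjusted biomarker-response analysis is put at risk.

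**What to change.** Replace the covariate sentence in section 7.5.2 with wording such as:

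> The EGFR, apoptosis and DNA-repair markers are the pre-specified candidate markers, each analysed one at a time; any adjusted model has at most one pre-named covariate; logistic models use Firth-penalised or exact estimation.

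This keeps the priority given to these markers, agrees with section 7.2, leaves the t-test and log-rank comparisons unadjusted, and reconciles the sentence with optional adjustment. Firth or exact estimation is still needed with one marker at a time, because a single binary marker separates the data in 3-13% of cases.

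The cost is wording only, with no added patients, samples or visits. The multi-marker adjusted logistic model is lost, but the data cannot support it. The one-covariate limit as worded also reaches the Cox model. The figures here do not address that model, so if the sponsor wants a larger one it should state a separate limit tied to the number of PFS events.
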